- M A negative assay outcome must be documented within 6 weeks of dosing. Should there be any problems with testing, it is acceptable to take repeat samples during the screening period as necessary.
- N Vit D, Fe²⁺ and Vit B12 at screening only.
- O Serology will be conducted by a central laboratory and will screen for; HepB (surface antigen), HepC (antibody and RNA) (HepC RNA PCR only indicated for a positive HepCAb screen), HIV 1 and 2 antibodies. CMV IgG testing followed by CMV DNA PCR (CMV PCR only indicated for a positive CMV IgG).
- P In the event of an increase in ALT an additional plasma GCase sample should be taken.
- Q Samples will be taken three times within 7-10 days after FLT201 infusion then weekly until the results from all matrices are negative at three consecutive visits. Collection of a particular matrix sample, e.g., plasma, can be stopped once negative results have been reported in that matrix at three consecutive visits at least 1 week apart after Week 1. Collection of the remaining matrices should continue until each delivers negative results at three consecutive visits at least 1 week apart after Week 1. Semen samples may be omitted at the discretion of the investigator for religious or other personal reasons expressed by the subject.
- R In the event of participant discontinuation/withdrawal, every effort should be made to complete Week 38/EOS procedures.
- S Minimum requirements for unscheduled visits are shown in the table. Additional assessments may be performed at the discretion of the investigator. A pregnancy test is only required if both (a) the unscheduled visit is 4 weeks or longer from previous pregnancy test and (b) viral shedding results are not negative at three consecutive visits taken at least 1 week apart after Week 1 in all matrices.

Table 2: Detailed Schedule of Assessment for Day -1 to Day 3 (Infusion Week)

Procedure ^A	Day -1 ^C	Day 1 (Infusion Day)										Day 2	Day 3
		Pre-dose ^B	Timepoint (min) during infusion		Timepoint (hours) from end of infusion								
			-1h	0	Every 15 min	+1	+2	+3	+4	+5	+6		
Window	-2 days	-	-	± 5 min	± 5 min	± 10 min					± 15 min	-	-
Prior & concomitant medications	X	X	X	Every 15 min	X	X	X	X	X	X	X	X	X
Physical examination	X ^{D, E}											X	X
Vital signs ^F	X	X		Every 15 min	X	X	X	X	X	X	X	X	X
12-lead ECG	X											X	
FLT201 administration			X	----->									
Adverse events	X	X	X	Every 15 min	X	X	X	X	X	X	X	X	X
BPI-SF, FACIT-Fatigue, diary completion	X												

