12.3 Week 38/End-of-Study Visit

The following assessments will be conducted at Week 38. Should the participant discontinue the study at an earlier time point, every attempt should be made to conduct the Week 38 assessments to ensure adequate safety follow-up.

- AE and concomitant medication status.
- Gaucher disease severity (GD-DS3).
- Physical examination.
- Vital signs (pulse, blood pressure, respiration rate, and temperature).
- 12-lead ECG.
- Urine pregnancy test (serum confirmation if positive urine test).
- Local laboratory analysis LFTs.
- Abdominal and bone MRI.
- Chest x-ray and pulmonary function tests.
- DEXA Z-score and T-score; lumbar spine and hip.
- Participants will be asked to complete an electronic diary commencing at week 37 for 7 consecutive days, completing the following questionnaires:
 - BPI-SF during the last 24 hours – daily for 7 days prior to this visit
 - FACIT-Fatigue during the last 7 days recorded on Day 7 of the diary completion

Study sites will contact participants at the beginning of Week 37 to remind them to complete the questionnaires during Week 37.

- Blood samples will be collected to evaluate (central laboratory analysis):
 - AAVS3 immune response.
 - Haematology, chemistry (including hs troponin-T and LFTs).
 - GCaSe activity level.
 - GCaSe concentration.
 - GCaSe immune response.
 - Lyso-Gb1.
 - Chitotriosidase, CCL18, bsALP, osteocalcin.
 - Research plasma sample.
- Plasma, saliva, urine, stool, (and semen, male participants only) samples will be taken for PCR of vg. Collection of a particular matrix sample, e.g., plasma, can be stopped once negative results have been reported in that matrix at three consecutive visits at least 1 week apart after Week 1. Collection of the remaining matrices should continue until each delivers negative results at three consecutive visits at least 1 week apart after Week 1.
- HRQoL will be evaluated using the SF-36 questionnaire.

On completion of the study, participants will be followed under a separate long-term follow-up protocol for at least a total of 5 years after dosing.

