12.7 Study Withdrawal

Participants are free to withdraw from the study, at any time, without prejudice to their continued care. The reason for discontinuation/withdrawal must be determined by the investigator and recorded in the participant's medical record and in the eCRF. If a participant is withdrawn for more than one reason, each reason should be documented in the source document and the most clinically relevant reason should be entered in the eCRF.

Reasons for withdrawal include but are not limited to:

- Protocol violation
- Withdrawal by participant
- Death
- Lost to follow-up
- Other (If "other" is selected, the investigator must specify the reason on the eCRF).

If a participant expresses their wish to withdraw from the study, the investigator should explain the importance of remaining on study follow-up, or failing this, of allowing routine follow-up data to be used for study purposes.

In the event of early withdrawal/discontinuation, every effort should be made to collect data in line with Week 38/EOS assessments.

If a participant relocates from the area, every effort should be made for the participant to be followed up at another participating study site and for this new site to take over the responsibility for the participant, or for follow-up via the participant's general practitioner.

The investigator should contact the Sponsor to discuss the withdrawal of any participant.

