15.7 Protocol Deviations

There will be no Per Protocol analysis and as such protocol deviations will be listed. The impact of any major protocol deviations will be noted in the summary statistics for specified outcomes that will be defined in the SAP.

All protocol deviations are to be recorded with the indication of whether they are major as determined by the study management team, in cooperation with data management, medical monitoring, and the Sponsor. These data will be imported into SAS, including the assignment of minor or major. A review of the protocol deviations will be performed before database lock. Assessment windows for observations will be defined in the SAP.

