## **4. General Statistical Considerations**

All study data collected will be presented in data listings, and all relevant data will be tabulated and summarized by study part, dose cohort, and overall, unless stated otherwise.

Continuous data will be described using descriptive statistics (i.e., n, mean, standard deviation, median, minimum, and maximum). Categorical data will be described using the count and percentage in each category. For the summary statistics of all numerical variables unless otherwise specified, minimum and maximum will be displayed to the same level of precision as reported. Mean and median will be displayed to one level of precision greater than the data collected. Standard deviation, standard error, and confidence intervals will be displayed to two levels of precision greater than the data collected.

Missing data will not be imputed. All analyses will be based on observed cases for the safety population unless specified otherwise.

Clinical laboratory and PK results that are below the lower limit of quantification (BLQ/LOQ), below the limit of detection (LOD), above the upper limit of quantification (ULOQ) or missing will be displayed as such in the data listings.

To calculate descriptive statistics and PK parameters, all BLQ, LOQ and LOD results will be treated as half of the BLQ/LOQ/LOD values whereas all ULOQ values will be treated as the ULOQ values as applicable.

The end of the study will be defined as the last visit by the last participant. All participants will be followed up for at least 5 years in a separate long-term follow-up study.

Unless specified otherwise, baseline will be defined as the last non-missing measurement prior to the infusion of IMP.

Change from baseline is defined as: post-baseline value – baseline value.

Study Day 1 is the calendar day of the IMP infusion. Subsequent study days are calculated as the date of assessment/event – date of infusion + 1. Pre-infusion study days are calculated as date of assessment/event – date of infusion. There is no Study Day 0.

All data are summarized based on the visit name collected on the eCRF page.

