### **10.2. Plasma, Leukocyte, Dried Blood Spot GCase Activity**

Sample collections that have an actual sampling time that deviates from the predefined collection time windows will be flagged in the data listings.

The following visit windows will be applied for the GCase sample collections:

Screening: +/-1 week

Weeks 1 to 12: +/-1 day

Weeks 14, 16, 20, 24, 28, 32, 38: +/-3 days

Week 38: +/-1 weeks

Individual GCase activity levels will be presented in data listings. A summary statistic for observed and changes from baseline values will be presented by study part, matrix, cohort, and overall.

Individual GCase raw activity levels will be plotted by-participant over time.

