### **10.3. Plasma, Leukocyte and DBS Pharmacokinetic Parameters**

Plasma, leukocyte, and DBS GCase baseline adjusted activity level-time data will be analyzed by non-compartmental analysis using Phoenix® WinNonlin® Version 8.3 or higher (Certara USA, Inc., Princeton, NJ). The following PK parameters will be calculated for baseline adjusted GCase activity levels, where data permit:

$C_{\max}$	Maximum observed concentration.
$T_{\max}$	Time of maximum observed concentration.
$AUC_{\text{last}}$	AUC from time 0 to the last measurable observed concentration ( $C_{\text{last}}$ ), calculated using the linear trapezoidal rule.

Actual sampling times will be used for the estimation of all PK parameters, and all available GCaSe activity level data will be included in the analysis (including resulting from samples collected outside predefined collection windows).

Plasma, leukocyte, and DBS PK parameters will be presented in data listings and summarized separately using descriptive statistics (number of observations, arithmetic mean, SD, CV, geometric mean, geometric CV, median, minimum, and maximum) by study part and cohort.  $T_{\max}$  will be summarized using number of observations, median, minimum, and maximum only.

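### Unless the eCRF names early termination separately, an early-withdrawal assessment would be summarised as a Week 38 result, because the protocol has one combined Week 38/EOS visit and the SAP summarises by visit name

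*SAP*

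**What the plan says.** **How data are assigned to visits.** SAP 4: "All data are summarized based on the visit name collected on the eCRF page". The same section defines study day but does not use it to assign visits. It also says that missing data are not imputed and that analyses use observed cases.

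**What happens on early withdrawal.** Protocol Table 1 has one combined 38/EOS column with a window of ±2 weeks. Its footnote R says: "In the event of participant discontinuation/withdrawal, every effort should be made to complete Week 38/EOS procedures". Protocol 12.3 says: "Should the participant discontinue the study at an earlier time point, every attempt should be made to conduct the Week 38 assessments". Protocol 12.7 repeats that "every effort should be made to collect data in line with Week 38/EOS assessments". The only other off-schedule column in Table 1 is for unscheduled visits.

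**Windows.** Protocol 15.7 says: "Assessment windows for observations will be defined in the SAP". The SAP has windows in one place, section 10.2, for GCase activity samples. Their stated use is: "Sample collections that have an actual sampling time that deviates from the predefined collection time windows will be flagged in the data listings". Week 38 appears there in the ±3 days list and again as "Week 38: +/-1 weeks". For the PK parameters, SAP 10.3 says: "Actual sampling times will be used for the estimation of all PK parameters". SAP 14 lists four changes from the planned analysis. The absence of windows for all other assessments is not among them.

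**Regional schedules.** The SAP serves the global, US and Brazil protocols. SAP 7.2.2 puts the end-of-study visit at Week 38 outside the US and at Month 24 in the US.

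**The concern.** Each provision is ordinary alone. Together they leave an early-termination assessment with no destination except the combined Week 38/EOS label, and the SAP tabulates by label. A value taken well before Week 38 could then sit in the Week 38 row beside true Week 38 values. In effect it would be carried forward, although the SAP says that nothing is imputed.

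Such a value may also differ in kind. Under protocol 8.1, Part 1 participants stay on ERT/SRT until at least two consecutive qualifying leukocyte GCase results from 4 weeks post-dosing onwards. Under protocol 10.4, prophylactic immunosuppression starts at about Week 3 and tapers over many weeks. An early assessment can fall within either period.

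The study is descriptive with very small cohorts, so the by-visit tables of change from baseline are the main efficacy output. DEXA and SF-36 are most exposed, because Week 38/EOS is their only scheduled post-baseline assessment.

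**Working it through.** The plan states no figure to reproduce. The check is of the text, with simple arithmetic for size.

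**1. Can the stated rules produce the result?** Sites attempt the Week 38/EOS assessments when a participant leaves early (Table 1 footnote R; protocol 12.3 and 12.7). Neither document names another visit for them. SAP 4 then summarises by visit name, and no later SAP section reassigns, relabels or excludes an out-of-window value from the by-visit summaries. So the result follows, unless the eCRF has an early-termination visit name.

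**2. Window in study days.** SAP 4 counts the infusion day as Day 1, so Week 38 = 38 × 7 + 1 = Day 267. Table 1 gives 267 ± 14 = Days 253 to 281. The synopsis gives 38 weeks with a +2-week window, which read literally is Days 267 to 281.

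**3. Displacement.** Assume withdrawal at Week 10. The value is 38 − 10 = 28 weeks early, and 36 − 10 = 26 weeks before the Table 1 window opens. Immunosuppression could run to about Week 3 + 3 + 11 = 17 or 3 + 3 + 13 = 19, so a Week 10 value could fall inside the taper.

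**4. Weight of one value.** Its share of a mean is 1/n:

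| n | Share |
|---|---|
| 1 | 100% |
| 2 | 50% |
| 3 | 33.3% |
| 12 (Part 1) | 8.3% |
| 18 (all) | 5.6% |

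**5. Illustration with assumed values.** Two completers each change by −40% at Week 38. A third participant's early value of −10%, −20% or −30% gives a reported mean of (−40 − 40 − 10)/3 = −30.0%, or −33.3%, or −36.7%. The completers' mean is −40%.

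**6. Chance that it arises.** The documents give no dropout rate. With an assumed independent rate d, P(at least one early withdrawal) = 1 − (1 − d)^n:

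| d | n = 12 | n = 18 |
|---|---|---|
| 5% | 46% | 60% |
| 10% | 72% | 85% |
| 20% | 93% | 98% |

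This treats every participant as having the combined visit. US participants do not, so the chance for the combined visit is lower if some are enrolled there.

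**7. GCase windows.** A Week 38 sample 4 to 7 days off target is flagged under ±3 days and not under ±1 week. One 8 to 14 days off complies with Table 1 and is flagged under both. SAP 10.2 also sets screening at ±1 week. That matches the tolerance of Screen 2 (−3 weeks ±1 week), whereas Table 1 as extracted places screening GCase activity at Screen 1 (−16 to −2 weeks).

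**The case against.** **The eCRF is unseen.** The problem arises only if early-termination data are filed under the Week 38/EOS name. This stands, and it makes the conclusion conditional. It does not remove the need for a rule, because neither document mentions a separate name and protocol 15.7 left windows to the SAP.

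**The protocol asks only for an effort.** Protocol 12.3 gives adequate safety follow-up as the purpose, and assessment at the time of withdrawal is implied rather than stated. This stands: the early value may not exist. If it does, the labelling question is the same.

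**The tables are descriptive and the data traceable.** All data are listed, and SAP 5.1 lists early discontinuations with dates and reasons. Lyso-Gb1 and organ volumes (SAP 8.3) and haemoglobin and platelets (SAP 9.2.1) are plotted by participant over time. Listings would show the true timing, as would plots drawn on actual time, which SAP 8.3 and 9.2.1 do not specify. No such plots are planned for DEXA or SF-36. This limits the harm, but the summary tables would still be wrong.

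**Cohorts may be expanded beyond 3.** True, so 33% to 100% applies to cohorts of the planned size only.

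**The two Week 38 windows in SAP 10.2 may reflect regional schedules.** Possible, since the US protocol is not among the documents. The SAP does not say so.

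A reader might infer that the conflicting GCase windows distort the PK results or turn compliant samples into protocol deviations. The documents do not support this. The windows flag listings, deviations are reviewed separately (protocol 15.7, SAP 5.2), and PK parameters use actual times and all available samples.

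**Conclusion.** The gap is real, and the SAP should close it. As written, the plan would summarise an early-withdrawal value as Week 38 for lyso-Gb1, spleen and liver volume, haemoglobin, platelets, DEXA and SF-36. One value would supply 33% to 100% of the mean in a planned cohort of 1 to 3. This rests on three assumptions: at least one participant leaves early, the assessments are done at that time, and the eCRF has no separate early-termination name.

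A reader might go further and infer that early values will certainly be reported as Week 38, or that the trial's main conclusions are compromised. Neither follows. The first depends on the unseen eCRF and on withdrawals that may not occur. As to the second, the primary endpoint is TEAE incidence to the last follow-up visit and does not use the Week 38 label. GCase Cmax and Tmax are not mis-timed; AUClast also uses actual times, though it would cover a shorter period in an early leaver. DEXA and SF-36 are exploratory.

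The duplicate Week 38 entry in SAP 10.2 is a separate, smaller inconsistency. It holds whether or not anyone withdraws, and it affects listing flags only.

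**What to change.** **SAP 4.** State that an EOS assessment done outside the protocol's Week 38 window, judged by study day, is summarised in a separate early-termination row and excluded from Week 38 summaries. Take the window from Table 1 (Days 253 to 281) after reconciling it with the synopsis. Apply the equivalent rule to the US Month 24 EOS visit. If the eCRF already has an early-termination name, say so in the SAP.

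Moving such values to the nearest scheduled visit is not a sound alternative. DEXA and SF-36 have no other post-baseline visit. For MRI and lyso-Gb1, the midpoint between Weeks 24 and 38 is Week 31, so a withdrawal at Weeks 32 to 35 is nearest to Week 38 yet outside its window. For haemoglobin and platelets, it could place two values in one visit and bring in the worst-value rule of SAP 9.2.

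**SAP 10.2.** Remove the duplicate Week 38 entry and align the Week 38 and screening GCase windows with each regional protocol's schedule. In global Table 1 these are ±2 weeks for Week 38, and Screen 1 for screening GCase activity.

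**Cost.** SAP wording and a visit-mapping step in programming, with no new data. The number of participants summarised at Week 38 may be smaller.

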#### **4.1. Date Imputations**

For the purpose of inclusion in prior and/or concomitant medication/procedure and AE tables, incomplete medications/procedures and AEs start, and end dates will be imputed as follows:

Missing start dates (where UK, UKN and UNKN indicate unknown or missing day, month, and year respectively):

- UK-MMM-YYYY: If the month and year are different from the month and year of the IMP infusion, assume 01-MMM-YYYY. If the month and year are the same as the IMP infusion month and year and the end date (after any imputation) is on or after the IMP infusion, then assume the date of the IMP infusion. If the month and year are the same as the IMP infusion month and year and the end date (after any imputation) is prior to IMP infusion, then assume the end date for the start date.
- DD-UKN-YYYY/UK-UKN-YYYY: If the year is different from the year of the IMP infusion, assume 01-JAN-YYYY of the collected year. If the year is the same as the IMP infusion year and the end date (after any imputation) is on or after IMP infusion, then assume the date of the IMP infusion. If the year is the same as the IMP infusion and the end date (after any imputation) is prior to the IMP infusion, then assume the end date for the start date.

Missing end dates (where UK, UKN and UNKN indicate unknown or missing day, month and year respectively):

- UK-MMM-YYYY: Assume the last day of the month.
- DD-UKN-YYYY/UK-UKN-YYYY: Assume 31-DEC-YYYY.

For prior/concomitant medication, if start date is completely missing and end date is not prior to the IMP infusion, then the medication will be classified as both prior and concomitant. If the start date is completely missing and the end date is within 30 days prior to the IMP infusion, then the medication will be classified as prior. If the end date is missing, then the medication will be classified as ongoing. Medications for which the start and end dates are missing will be classified as prior and concomitant.

## **4.2. Sample Size**

Sample size is based on feasibility and not formal hypothesis testing. All statistical analysis will be descriptive.

It is planned to include approximately up to 12 participants into Part 1 and approximately 6 participants in Part 2 (excluding US participants). The actual number of participants will depend on emerging data.

The dose escalation scheme as described is intended to minimize the number of participants that may be dosed at suboptimal levels, whilst allowing for safety evaluation and option to expand each cohort where DLT is observed.

## **4.3. Randomization, Stratification, and Blinding**

This is an open-label study; therefore, participants will not be randomized, stratified or blinded.

## **4.4. Analysis Set**

### **4.4.1. Screened Set**

The Screened Set will include all participants with recorded data in the database, including screen failures.

### **4.4.2. Safety Set**

The Safety Set will include all participants who received any dose of FLT201. This population will be used to report both Parts 1 and 2. All data summaries will use the Safety Set, unless otherwise specified.

### **4.4.3. Pharmacokinetic (PK) Set**

The Pharmacokinetic (PK) Set will include all participants who received any dose of FLT201 and had had at least one measurable GCase activity level result for leukocyte, plasma or DBS data.

Where participants experience issues which may affect GCase activity level (e.g., dosing errors), data will be reviewed by the study pharmacokineticist and evaluated for exclusion from the PK Set on a case-by-case basis. All participants excluded from the PK Set will be documented in the data listings.

## 5. Participant Disposition

### 5.1. Disposition

Participant disposition will be summarized for the Screened Set. The number and percentage of participants enrolled, dosed participants, participants who completed the study, and participants who prematurely discontinued study (i.e., withdrawal) will be presented. Primary reasons for discontinuation of individual participants may include any of the following:

- Adverse Event
- Death
- Lost to Follow-up
- Physician Decision
- Protocol Violation
- Trial Screen Failure
- Trial Site Terminated by Sponsor
- Study Terminated by Sponsor
- Withdrawal by Subject
- Other

Participant disposition data (including subject identifier, informed consent date, date of dose, date of study completion/termination, and, for those who discontinued study early, the specific reason(s) for discontinuation will be presented in a listing for the Screened Set.

A listing of all participants that failed screening will be presented for the Screened Set.

